The COVID-19 crisis has undoubtedly affected biobehavioral research. Older adults and those with chronic health problems are at greater risk for increased severity of symptoms and poor outcomes compared to younger populations or those without chronic health problems. Thus, our sample of women aged 65 years and older with cardiovascular disease (CVD) are considered a high-risk population during the current pandemic. We anticipate that we may face significant challenges if we were to follow the original protocol. Overall, our goal is to successfully fulfill the aims of the original proposed study, following the original timeline while keeping our participants and research staff safe. However, we realize that the current pandemic will have lasting effects for our patient population even as risk of infection declines. Our patient population may not feel comfortable coming to the clinic for study visits or attending in-person intervention group meetings despite the initial pandemic being over. Thus, we will have

alternative methods that can enable our team to successfully conduct the study. In this protocol, we will compare our original strategies versus the alternative strategies that will be utilized to decrease risk to patients throughout screening, data collection, and the intervention. Our alternative strategies aim to accommodate older women who may be at risk to leave the home after the current restrictions are lifted, or may feel more comfortable avoiding the clinic setting.

B. Recruitment and Screening

Participants ($N = 254$) are women ≥ 65 years with CVD, who are recruited from the Rush Heart Center for Women (Center). The Center was the first heart program in Chicago devoted exclusively to women. There are two modes of entry into the study: (1) referral by the Center cardiology provider; (2) participants will self-refer for participation in the study after reviewing study materials posted at the Center clinic sites; and (3) patients who are 65 years or older, women, and have seen the Rush cardiology practice since March 2019 will be mailed letters introducing the study. All participants require approval from their cardiology provider. Approval will be obtained using the parmedx questions, that will be sent via redcap link in the Epic messaging. The parmedx allows providers to select if they approve of a patient's participation in a moderate physical activity program.

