Original secondary screening. At the beginning of the secondary screening appointment, the data collector will complete the informed consent and HIPAA research authorization process. The data collector will read the informed consent/authorization to the participant and the participant will have time to ask questions (10-15 minutes total). The informed consent and HIPAA research authorization process will be completed prior to any additional screening or data collection. During the informed consent and HIPAA research authorization process, participants will be asked for permission for the data collector to review the EHR for additional screening items. Following informed consent, participants will be screened for cognitive status (Montreal Cognitive Assessment), and will complete the Physical Activity Readiness Questionnaire. Data collectors will then review the EHR for the following criteria: diagnosis of CVD, blood pressure \leq 160 or diastolic \leq 100 mm Hg at the last clinic visit, hemoglobin A1C $<$ 9.0 in the past six months, no diagnosis of neurological disease, no stroke in the past three months, no stage 5 renal disease on dialysis, and medications (no anti-psychotics).

If a participant is not eligible for the study based on secondary screening, the participant is considered as a screen failure. Eligible patients who agree to participate and are eligible at all stages of screening will complete baseline data collection appointments, either directly following secondary screening, or at a separate appointment in a private room at RUMC or ROPH.

B2b. Alternative screening protocol.

Alternative secondary screening. We will both mail a paper copy as well as email a digital copy of the informed consent/authorization form to the patient following a positive preliminary screening appointment. We will complete the secondary screening appointment over the phone instead of in-person. At the beginning of the secondary screening appointment, the data collector will verify the patient's full name and date of birth to verify identify. Then the data collector will read the information consent/authorization to the participant, explaining all

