C2. Alternative Baseline (D1) Protocol. Baseline appointments (D1) will have both phone and in-person components. First in-person data collection will be scheduled. The in-person data collection appointment will occur in the participants' home. Prior to the in-person appointment, the data collector will ask if the participant or anyone that the participant is living with has symptoms of a respiratory infection including fever, shortness of breath, or cough. If the participant reports positive symptoms, then the in-person appointment will be rescheduled. The data collector will wear a gown, gloves, and mask to data collection appointments. At the in-person part of the appointment, participants will complete measurements of weight, height, BP, and step test, and the data collector will draw blood samples after an 8-hour fast between 8am and 10am²³⁵ for serum biomarker levels and genotyping. Either at the outpatient laboratory or in the participant's home, participants will prick their finger once to obtain 4 blood spots (with additional pricks if necessary to obtain the 4 blood spots), and smear those blood spots on a card, also for serum biomarker levels and genotyping. Both blood samples will be taken back to the Rush Biomarker Core for processing. Participants will wear an ActiGraph accelerometer on the hip to measure physical activity during waking hours for seven days, and then return the device to staff in a prepaid, padded envelope with tracking information. Return demonstration will be used to ensure proper accelerometer placement. Participants will receive a reminder text message and phone call two days following the data collection appointment to remind them to wear the accelerometer. Participants will be given a questionnaire response booklet that will be used during the phone data collection component.

Then phone data collection will consist of the data collector administering questionnaires and performance-based neurocognitive tests.

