**NCT04556305**

**01.26.2021**

## STATISTICAL DESIGN AND POWER

### Power Analysis

**Power Analysis.** Power was estimated using design effect methods to account for clustering of cases within randomized cohorts. Due to the group meeting component of *Move*, participants will be randomized into groups of 10-11 participants. Assuming 24 cohorts of 10-11 participants each (6 cohorts per cell in the 2x2 factorial design; Figure 3), a 15% attrition rate (a conservative estimate based on our previous results), and a correlation of 0.7 between assessments of memory performance (as measured by neurocognitive tests), we estimate 80% power to detect an interaction effect ( $d = 0.30$ ) for significance ( $p < 0.05$ ) with  $N = 254$  participants (216 after accounting for attrition). This is a reasonable minimal effect size for the interaction effect described in Aim 1. Although existing systematic reviews suggest an estimated effect size of  $d = 0.50$ , we estimate  $d = 0.40$  given our previous work as a more conservative estimate for the main effects of the *Move* and *Mind* interventions. Assuming an effect size of  $d = 0.40$ , our study design has > 90% power. Thus, 254 women with CVD will be recruited (63-64 in each cell).

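### The blood pressure criterion joins its two limits with 'or', so as written it excludes only women who exceed both; it should say 'and'

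*Protocol*

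**What the plan says.** In the protocol's B2a (original secondary screening), the data collector opens the health record after consent and checks a list: "Data collectors will then review the EHR for the following criteria: diagnosis of CVD, blood pressure" at or below "160 or diastolic" at or below "100 mm Hg at the last clinic visit". The list continues with haemoglobin A1C under 9.0 and then "no diagnosis of neurological disease, no stroke in the past three months, no stage 5 renal disease on dialysis". B2b (alternative secondary screening, done by telephone) repeats the blood pressure item with the same connector. The first limit is not labelled systolic in either place.

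Both sections give the consequence of failing: "If a participant is not eligible for the study based on secondary screening, the participant is considered as a screen failure".

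Other parts of the protocol bear on the same risk. Section B says "All participants require approval from their cardiology provider", and describes that approval as clearance for a moderate physical activity programme. B2a and B2b also call for the Physical Activity Readiness Questionnaire. In the alternative baseline (C2) and alternative follow-up (C5) procedures, "participants will complete measurements of weight, height, BP, and step test". The SAP's Power Analysis plans "63-64 in each cell".

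**The concern.** A ceiling on systolic pressure and a ceiling on diastolic pressure protect a participant only if each works on its own. With 'or' in a list of conditions to be met, neither does: a woman with very high systolic pressure qualifies if her diastolic is within range, and the reverse.

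What is at stake is safety screening and consistent enrolment. The population is women aged 65 or over with cardiovascular disease. Women in the *Move* and *MindMoves* cells are given a moderate-intensity activity goal, and under the alternative procedures women in every cell do a step test. Blood pressure is measured again at baseline (C1, C2), but no limit or action is attached to that reading. The wording also leaves room for one data collector to apply the literal rule and another the presumed intent, and enrolling a woman under the literal rule could not be called a protocol deviation.

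**Working it through.** The plan gives no figure to reproduce; this is a check of logic.

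**Inputs** (protocol B2a, repeated in B2b)
- First limit: ≤ 160, read as systolic (S).
- Second limit: diastolic (D) ≤ 100 mm Hg.
- Connector: 'or'.
- Timing: most recent clinic visit.

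**Step 1: which way the list runs.** The neighbouring items are a CVD diagnosis, A1C below 9.0, and a series of 'no' conditions. Each must be true for a woman to be eligible. The blood pressure item sits among them and uses ≤, so it too is a condition to be met. 'Or' would be correct only for an exclusion, that is, exclude if S > 160 or D > 100.

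**Step 2: who fails.** A woman fails when the condition is false:

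not (S ≤ 160 or D ≤ 100) = (S > 160 and D > 100)

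Checking this over every whole-number reading with S from 80 to 260 and D from 40 to 160 gave 0 mismatches. Under 'and', the failing set becomes S > 160 or D > 100.

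**Step 3: example readings.**

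| Reading | Eligible under 'or' (as written) | Eligible under 'and' |
|---|---|---|
| 150/90 | yes | yes |
| 160/100 | yes | yes |
| 190/95 | yes | no |
| 150/110 | yes | no |
| 161/101 | no | no |
| 190/110 | no | no |

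Of the four combinations of S within or over its limit and D within or over its limit, three pass as written and one passes under 'and'. This counts logical categories, not patients.

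**Step 4: planned exposure to the activity programme.** Two of the four cells contain *Move*: 2 × 63 = 126 to 2 × 64 = 128 of 254 women. This is the size of the group assigned to the programme. It is not the number who would be over one limit, for which the documents give no basis.

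**The case against.** The strongest reply is that this is a slip of drafting and not a decision to admit women at 190/95. Staff working with cardiology providers would probably read the line as two ceilings. Every participant also needs her cardiology provider's approval for moderate activity, and a clinician who knows the patient does not need a printed number to hold back someone with uncontrolled hypertension. The readiness questionnaire is a further check.

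It can also be said that B2a and B2b may only summarise screening. They name the Montreal Cognitive Assessment without a cut-off, and the consent checklist refers to inclusion and exclusion criteria as if a formal list exists elsewhere. The protocol text under review starts at section 4.2, so a correctly worded list may exist outside it. Finally, the criterion is applied before randomization and cannot bias the comparison.

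Much of this stands. The intent is inferred, the other safeguards are real, the number affected is unknown, and the trial's inference is not at risk. None of it makes the two sentences right. They are instructions to the people doing the screening, with a stated consequence for failing. The other checks have no stated blood pressure limit that would take the place of this one. If a correct list exists elsewhere, these sections contradict it and need the same edit.

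**Conclusion.** The concern holds. As written in B2a and B2b, the criterion excludes only women above 160 systolic and above 100 diastolic together; a woman over one limit alone qualifies. The logic follows from the text and needs no outside figure.

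The conclusion rests on three readings: that the unlabelled first limit is systolic, that both limits were meant to apply (inferred from the purpose of such a limit, not stated), and that no correct version stands elsewhere in the protocol text under review (none was found). Its practical size is unknown and is softened by provider approval and the readiness questionnaire. It should be corrected as a matter of safety screening and clear eligibility. Sample size, power and the between-arm comparison do not change.

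**What to change.** In both B2a and B2b, replace the blood pressure item with: systolic blood pressure ≤ 160 mm Hg **and** diastolic blood pressure ≤ 100 mm Hg, leaving the timing of the reading as it is. The equivalent exclusion is systolic > 160 mm Hg **or** diastolic > 100 mm Hg. Use one form throughout, and bring any screening form or formal eligibility list into line with it.

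The cost is one short wording change in two places. Women over exactly one limit would now fail screening, so a few more screen failures are possible.

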**NCT04556305**

**01.26.2021**

## STATISTICAL DESIGN AND POWER

### Power Analysis

**Power Analysis.** Power was estimated using design effect methods to account for clustering of cases within randomized cohorts. Due to the group meeting component of *Move*, participants will be randomized into groups of 10-11 participants. Assuming 24 cohorts of 10-11 participants each (6 cohorts per cell in the 2x2 factorial design; Figure 3), a 15% attrition rate (a conservative estimate based on our previous results), and a correlation of 0.7 between assessments of memory performance (as measured by neurocognitive tests), we estimate 80% power to detect an interaction effect ( $d = 0.30$ ) for significance ( $p < 0.05$ ) with  $N = 254$  participants (216 after accounting for attrition). This is a reasonable minimal effect size for the interaction effect described in Aim 1. Although existing systematic reviews suggest an estimated effect size of  $d = 0.50$ , we estimate  $d = 0.40$  given our previous work as a more conservative estimate for the main effects of the *Move* and *Mind* interventions. Assuming an effect size of  $d = 0.40$ , our study design has > 90% power. Thus, 254 women with CVD will be recruited (63-64 in each cell).

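### The SAP's 80% interaction power states no ICC, reference distribution or degrees of freedom; if it is a normal-scale figure, it is about 76% on the 20 degrees of freedom that 24 cohorts leave.

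*SAP*

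**What the plan says.** The SAP's Power Analysis section says "Power was estimated using design effect methods to account for clustering of cases within randomized cohorts". Its stated inputs are these:

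- Clusters: "Assuming 24 cohorts of 10-11 participants each", with "6 cohorts per cell in the 2x2 factorial design".
- Loss to follow-up: "a 15% attrition rate", taking 254 recruited to 216 analysed.
- A correlation of 0.7 between memory assessments, and a 0.05 significance level.

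From these, "we estimate 80% power to detect an interaction effect" of d = 0.30. For main effects at d = 0.40, "our study design has > 90% power".

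The section gives no ICC or design-effect value, does not say whether the test is referred to a normal or a t distribution, gives no degrees of freedom, and does not define what d compares for the interaction.

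In the SAP's Cluster-Level Model, the arm terms and clinic site enter only in the cohort-level equations, beside cohort random effects for intercept and slope. The text after the equations expects those random effects to be non-significant and drops them in that case. Protocol section C3 describes the randomisation as clustered. Neither document mentions a small-sample correction for the number of cohorts.

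**The concern.** When cohorts are assigned to arms, an arm contrast is judged against the variation between cohorts. Two separate things then reduce power. The variance is larger, which the design effect covers. That variance is also estimated from few units, which the design effect does not cover. With 24 cohorts in 4 cells, the two-sided 5% critical value is 2.086 (20 df), not 1.960.

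The interaction is part of the primary aim, and the 80% is the figure that the Power Analysis attaches to N = 254. If the second component was left out, that figure is somewhat too high. The same gap affects the analysis. Referring an arm x time statistic that has 20 df to a cutoff of 1.96 gives a true two-sided size of about 6.4%. Dropping the cohort random effects takes the test off cohort-level degrees of freedom altogether.

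**Working it through.** **Inputs from the SAP.** 24 cohorts, 6 in each of 4 cells; 254 x 0.85 = 215.9, so 216 analysed; 216/24 = 9 per cohort; r = 0.7; alpha 0.05; d = 0.30 (interaction) and 0.40 (main effects).

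**Assumptions, because the SAP is silent.** Two-sided test. d compares two halves of 108 (a +1/-1 factorial contrast). ICC between 0 and 0.05, applied to the analysed quantity, so the design effect is 1 + (9 - 1) x ICC. Variance v in units of the outcome SD, for a single follow-up: change score 2(1 - 0.7) = 0.60; baseline-adjusted 1 - 0.7² = 0.51.

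**Formula.** Noncentrality = d / sqrt(v x (1 + 8 x ICC) x 4/216).

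**Step 1: the SAP's figure on the normal scale.** Change score, ICC 0: 0.30 / sqrt(0.60 x 4/216) = 2.846, power 81.2%. It is 80.0% at ICC 0.004 and 78.2% at ICC 0.01. Baseline-adjusted, ICC 0: 3.087, power 87.0%; 80% is reached at an ICC of about 0.027. The stated 80% can therefore be reproduced, but only by choosing an ICC that the SAP does not give.

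**Step 2: degrees of freedom.** 24 cohorts - 4 cells = 20; one more for clinic site leaves 19.

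**Step 3: conversion.** Power of 80% on the normal scale means a noncentrality of 1.960 + 0.842 = 2.802. The noncentral t distribution with that value gives 76.0% on 20 df and 75.7% on 19 df. If the 80% came from a person-level t test instead, the result on 20 df is 76.3%. This step does not depend on the ICC, the correlation or the coding of d.

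**Step 4: detectable effect.** 80% on 20 df needs a noncentrality of 2.945. So d = 0.30 x 2.945/2.802 = 0.315, and the extra information needed is (2.945/2.802)² - 1, about 10.5%. On 19 df, d = 0.316.

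**Step 5: absolute power on 20 df, single follow-up.**

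| ICC | d = 0.30, baseline-adjusted | d = 0.30, change score | d = 0.40, baseline-adjusted | d = 0.40, change score |
|---|---|---|---|---|
| 0 | 84% | 77% | 97% | 95% |
| 0.01 | 81% | 74% | 96% | 93% |
| 0.02 | 78% | 71% | 95% | 92% |
| 0.03 | 75% | 68% | 94% | 90% (89.98%) |
| 0.05 | 70% | 63% | 91% | 86% |

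**Step 6: using all three follow-ups.** The SAP's Statistical Analyses section offers a time term coded 0, 1, 1, 1. With r = 0.7 between all assessments and no extra random-slope variance (both assumed), v = (1 + 2 x 0.7)/3 + 1 - 2 x 0.7 = 0.40. On 20 df, d = 0.30 then has 91% power at ICC 0, 87% at 0.02 and 80% at 0.05. Random-slope variance would lower these figures.

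**Step 7: the scale of d.** If d = 0.30 is instead a difference of differences, the noncentrality halves. Normal-scale power before any clustering is then about 30% (change score, 1.423) or 34% (baseline-adjusted, 1.543).

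**The case against.** A reader might infer that the sponsor's calculation ignored the number of cohorts, or that the trial does not have 80% power. The documents support neither reading.

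On the method, the SAP names design effect methods but no reference distribution, and an inflated variance can still be referred to a t distribution on cohort-level degrees of freedom. A baseline-adjusted calculation already on 20 df gives 80% at an ICC of about 0.012, so it cannot be ruled out. What points the other way is circumstantial. Neither document mentions cohort-level degrees of freedom, and the change-score version gives close to 80% on the normal scale but at most 77.3% on 20 df.

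On the absolute power, nor can one say that 80% holds only with baseline adjustment and a very small ICC. The planned model uses four assessments, and under the assumptions of Step 6 the 0, 1, 1, 1 contrast still reaches 80% on 20 df at ICC 0.05.

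It is also fair to say that four percentage points is a small loss, that no arithmetic error in the SAP has been shown, and that the missing ICC and the undefined scale of d can move the power by more. All of that stands. It makes the point conditional and modest. It does not answer the gap in reporting, and it does not remove the need to fix the degrees of freedom for the analysis.

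**Conclusion.** The point holds as a conditional one. The SAP gives too little to tell which distribution lies behind the 80%. If it is the normal or a person-level t distribution, the interaction power on cohort-level degrees of freedom is about 76%, and the effect detectable with 80% power is about 0.315 rather than 0.30. That conversion rests only on 24 cohorts in 4 cells and a two-sided 5% test.

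The absolute power remains open. For a single follow-up, with d comparing 108 v 108 and ICC from 0 to 0.05, it runs from 84% to 70% baseline-adjusted and from 77% to 63% for a change score. A contrast averaging the three follow-ups would be higher. The main-effect claim holds across that ICC range when baseline-adjusted; as a change score it falls to the 90% line at ICC 0.03 and to 86% at 0.05. This is worth correcting in the SAP, but it is not a reason to question the sample size.

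**What to change.** In the SAP's Power Analysis section:

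- State the ICC, what d compares for the interaction, and the reference distribution used.
- Recompute on 20 cohort-level degrees of freedom, or 19 with clinic site.
- Restate either the interaction power (about 76% if the 80% was on the normal scale) or the detectable effect (about d = 0.32), with the range over plausible ICCs. If the calculation already used cohort-level degrees of freedom, saying so with the ICC is enough.

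In the Statistical Analyses section:

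- Specify Kenward-Roger or Satterthwaite degrees of freedom for the arm x time terms.
- Replace the rule that removes non-significant cohort random effects with one that keeps them regardless of significance. Naming a degrees-of-freedom method while leaving the removal rule in place would not bring analysis and power into line.

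N does not change. The cost is some SAP wording, a slightly less favourable stated power and slightly wider intervals.

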### Statistical Analyses

Under the direction of [name], all analyses will use an intent-to-treat approach (i.e., participants analyzed according to their assigned cell; **Figure 3**) independent of their actual dose of each intervention. All analyses will employ multi-level mixed models with repeated observations (baseline, 24, 48, and 72 weeks) nested within participants, and participants nested within cohorts. Three parameters for factorial design will be included in the models: (1) *Move* main effect, (2) *Mind* main effect, and (3) *Move* x *Mind* interaction effect. Time and interactions of time with the factorial design parameters will be included in the models. Potential covariates in the multi-level mixed models are in Table 5. Although many of these covariates may relate to memory level, they are generally less likely to influence change over time. Covariates will be at Level 2 (person level) or Level 1 (assessment level) as appropriate. To minimize the number of covariates in the final models, we will first test each candidate covariate individually in models for each memory outcome change over time (time x covariate interaction). We will retain only significant covariates in the final models.

Time can be handled flexibly with multilevel mixed models, allowing us to model hypothesized patterns of change over time that deviate from linear or quadratic patterns. For example, we expect that *Mind* effects will be greatest from baseline to 24 weeks, followed by a change plateau; thus, a parameterization of time would reflect a relatively large increase from baseline to 24 weeks followed by stabilization after 24 weeks. Adding a term for this discontinuity in memory level (coded 0, 1, 1, 1 for baseline, 24, 48, and 72 weeks, respectively) allows us to test this pattern. In contrast, for the *Move* effects, we expect a more gradual linear change in memory from baseline through 48-72 weeks; therefore, a discontinuity term may not be needed. The general multilevel mixed model for the proposed analyses can be represented by the following equations:

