#### Cluster-Level Model

$$\beta_{00k} = \gamma_{000} + \gamma_{001}(\text{Move}) + \gamma_{002}(\text{Mind}) + \gamma_{003}(\text{MindMoves}) + \gamma_{004}(\text{ClinicSite}) + u_{00k}$$

$$\beta_{01k} = \gamma_{010}$$

⋮

$$\beta_{04k} = \gamma_{040}$$

$$\beta_{10k} = \gamma_{100} + \gamma_{101}(\text{Move}) + \gamma_{102}(\text{Mind}) + \gamma_{103}(\text{MindMoves}) + \gamma_{104}(\text{ClinicSite}) + u_{10k}$$

$$\beta_{11k} = \gamma_{110}$$

⋮

$$\beta_{14k} = \gamma_{140}$$

$$\beta_{P0k} = \gamma_{P00}$$

Where

$\gamma_{000}$  is grand mean (intercept) for the outcome measure;

$\gamma_{001}$  through  $\gamma_{003}$  are the intervention main effects and interaction effect on the mean for the outcome measure;

$\gamma_{004}$  is the Clinic Site effect on the mean for the outcome measure;

$\gamma_{010}$  through  $\gamma_{040}$  are the overall effects for the person-level covariates;

$\gamma_{100}$  is grand mean change over time on the outcome measure;

$\gamma_{101}$  through  $\gamma_{103}$  are the intervention main effects and interaction effect on change over time for the outcome measure;

$\gamma_{104}$  is the Clinic Site effect on change over time for the outcome measure;

$\gamma_{110}$  through  $\gamma_{140}$  are the overall effects for the person-level covariates on change over time of the outcome measure;

$u_{0jk}$  is the cluster-level random effect for the intercept; and

$u_{1jk}$  is the cluster-level random effect for the time slope.

It is expected that the person-level random effects for the intercept ( $r_{0jk}$ ) and time slope ( $r_{1jk}$ ) will be significant (i.e., there will be significant between-person variation in level of the outcome and rate of change over time). Although we will include them in the initial models, it is likely that the cluster-level random effects for the intercept ( $u_{0jk}$ ) and time slope ( $u_{1jk}$ ) will be non-significant. If non-significant, those random effects will be removed from the models. The time-varying covariates include time of day for the assessment (i.e., for models with BDNF as the dependent variable – see Aim 2 below) and discontinuities (see above).

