**Aim 1 (primary): To determine the independent and combined efficacy of Move and Mind interventions on memory performance among women  $\geq 65$  years with CVD. Hypotheses: Move and Mind each will improve performance-based memory (main effects). In addition, there will be an interactive effect such that MindMoves will provide greater memory benefit than the sum of the main effects of Move and Mind.**

Aim 1 tests the main effects of the individual interventions (i.e., Move and Mind) as well as the interaction between the interventions. Outcome measures will be collected at baseline and 24, 48, and 72 weeks post-baseline. Because we hypothesize intervention effects on memory outcomes over time, significant Move x Time, Mind x Time, and Move x Mind x Time effects will provide evidence of significant main effects and a

significant interaction effect, respectively (parameters  $\gamma_{101}$ ,  $\gamma_{101}$ , and  $\gamma_{103}$  above).

Measures for Aim 1 (see section 4.3):

Primary Measures for Aim 1:

- [1] East Boston Memory Test (episodic memory)
- [2] Category Fluency (semantic memory)
- [3] Digit Span Forwards and Backwards (working memory)

Secondary Measures for Aim 1:

- [4] NIH Toolbox® Fluid Cognition Index (episodic memory, working memory, executive function, processing speed)

***Aim 2 (secondary): To determine the independent and combined efficacy of the *Move* and *Mind* interventions on memory-related serum biomarkers (brain-derived neurotrophic factor [BDNF], vascular endothelial growth factor [VEGF], insulin-like growth factor 1 [IGF-1]) among women  $\geq 65$  years with CVD. Hypotheses: *Move* and *Mind* each will improve serum biomarkers (main effects). In addition, there will be an interactive effect such that *MindMoves* will show a greater increase in biomarkers than the sum of the main effects of *Move* and *Mind*.***

Aim 2 tests the effects of *Move* and *Mind* individually (main effects) and combined (interaction effect) on memory-related serum biomarkers (BDNF, VEGF, IGF-1) at 24, 48, and 72 weeks post-baseline. Analyses will use multi-level mixed models as described in Aim 1. Due to known variation in BDNF levels throughout the day, time of day of assessment will be included as a time-varying covariate for analyses of impact on BDNF.

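### If d = 0.30 is the benefit of MindMoves beyond the sum of Move and Mind, the design does not give the stated 80% power, and the SAP does not say what d measures

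*SAP*

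**What the plan says.** The SAP's Power Analysis section assumes 24 cohorts of 10-11 women (6 per cell), 15% attrition and a correlation of 0.7 between assessments. From these it reports, for 254 recruited and 216 analysed, "we estimate 80% power to detect an interaction effect ( $d = 0.30$ ) for significance". It adds: "This is a reasonable minimal effect size for the interaction effect described in Aim 1". For the main effects it takes d = 0.40, "given our previous work as a more conservative estimate for the main effects of the" two interventions, and reports power above 90%. On method it says only: "Power was estimated using design effect methods to account for clustering of cases within randomized cohorts". No ICC or design effect is given.

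Aim 1 of the SAP puts the interaction hypothesis in words: "MindMoves will provide greater memory benefit than the sum of the main effects of Move and Mind". Protocol section 4.2 describes it in the same sense.

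The model sections do not fix the scale. Under Statistical Analyses, "Three parameters for factorial design will be included in the models", namely two main effects and their interaction. In the Cluster-Level Model the coefficients for change over time "are the intervention main effects and interaction effect on change over time for the outcome measure". The intercept "is grand mean (intercept) for the outcome measure", which leans towards effect coding, but no numeric coding and no unit of time is given.

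**The concern.** The interaction is part of the primary aim, and its 80% power is the stated basis for the sample size. Read with Aim 1, the sentence promises an 80% chance of detecting 0.30 SD of benefit beyond additivity. In a 2x2 design with equal cells, that excess is estimated with twice the standard error of a marginal main effect, so a power figure for an interaction means little until its contrast is named. If the 80% belongs to a different contrast, a null interaction could later be misread as evidence against a synergy of 0.30 SD that the trial had little chance of finding.

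**Working it through.** **Inputs from the SAP Power Analysis.** 254 x 0.85 = 215.9, so 216 analysed and 54 per cell; 216/24 = 9 per cohort; r = 0.7; alpha 0.05.

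**Assumptions, not in the documents.** Two-sided test; normal approximation; visit-level SD = 1; r = 0.7 between every pair of visits; design effect DE = 1 + 8 x ICC, with ICC 0 as the favourable case and 0.05 as an illustration.

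**Contrasts.** Let v be the residual variance per woman.
- Excess over additivity: S = MindMoves - Move - Mind + control, Var(S) = v x DE x 4/54 = v x DE x 16/216.
- Half-contrast: H = (MindMoves + control)/2 - (Move + Mind)/2 = S/2, Var(H) = v x DE x 2/108 = v x DE x 4/216.
- Hence SE(S) = 2 x SE(H), whatever v and the ICC are.

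**Residual variances.**
- Change score: 2(1 - r) = 0.60.
- Baseline-adjusted, one follow-up: 1 - r^2 = 0.51.
- Adjusted mean of three follow-ups: (1 + 2r)/3 - r^2 = 0.80 - 0.49 = 0.31.
- Linear slope over visits 0, 1, 2, 3: (1 - r)/5 = 0.06 per 24-week interval; 4 x 0.06 = 0.24 scaled to 48 weeks; 9 x 0.06 = 0.54 scaled to 72 weeks.

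**Can the 80% be reproduced?** With H = 0.30:
- Change score, ICC 0: SE = sqrt(0.60 x 4/216) = 0.105; power = Phi(0.30/0.105 - 1.960) = 81%.
- Baseline-adjusted: 87% at ICC 0. For 80%, v x DE must be (0.30/2.802)^2 x 54 = 0.619, so DE = 0.619/0.51 = 1.214 and ICC = 0.214/8 = 0.027. This is a back-solved fit, not a known value.
- Cross-check: 80% at 0.30 implies SE = 0.30/2.802 = 0.107. A main effect of 0.40 then has power Phi(0.40/0.107 - 1.960) = 96%, in line with the SAP's figure above 90%.

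A 54-v-54 comparison on the adjusted mean of three follow-ups also gives 79.9% at ICC 0 (SE = sqrt(0.31 x 8/216) = 0.107), although it is not an interaction contrast. The match therefore does not identify the source calculation.

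**Power if S = 0.30**

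| Analysis | v | SE(S), ICC 0 | Power, ICC 0 | Power, ICC 0.05 |
|---|---|---|---|---|
| Change score | 0.60 | 0.211 | 30% | 22% |
| Slope scaled to 72 weeks | 0.54 | 0.200 | 32% | 25% |
| Baseline-adjusted | 0.51 | 0.194 | 34% | 26% |
| Adjusted mean of three follow-ups | 0.31 | 0.152 | 51% | 39% |
| Slope scaled to 48 weeks | 0.24 | 0.133 | 61% | 48% |

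For 80%, v x DE would have to be (0.30/2.802)^2 x 216/16 = 0.155, below every row. A one-sided test would lift the last row at ICC 0 only to Phi(0.30/0.133 - 1.645) = 73%. The exception is a slope of 0.30 SD per 24-week interval: v = 0.06, SE = 0.067, power 99%. That is an excess of 3 x 0.30 = 0.90 SD by week 72.

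**Conversion if the 80% was computed on H.** SE(S) = 2 x 0.107 = 0.214. Power at S = 0.30 is Phi(0.30/0.214 - 1.960) plus a negligible lower tail, 29%. The excess detectable with 80% power is 2.802 x 0.214 = 0.60 SD. No ICC is needed for this step. If the source was instead the 54-v-54 comparison, SE(S) = sqrt(2) x 0.107 = 0.151, giving 51% and 0.42 SD.

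**Coding.** The model's interaction coefficient equals S under 0/1 or -0.5/+0.5 coding and S/4 under -1/+1. An S/4 of 0.30 has power over 99% for every v above at ICC 0. The coding also affects the main effects. At d = 0.40 and ICC 0, marginal effects (108 v 108) have 97% (change) or 98% (adjusted). Under 0/1 coding the Move and Mind terms are 54-v-54 simple effects, with 77% or 83%.

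**The case against.** The strongest reply is that nothing has been shown to be miscalculated. On the usual factorial-effect scale the section is coherent: one standard error of 0.107 gives 80% at 0.30 and 96% at 0.40. S is also an interpretation. The two marginal main effects add up to MindMoves minus control identically, so the Aim 1 sentence taken literally defines no excess; it has to be read with each effect taken against control. The tested parameter is a slope with no stated time unit, and for a short enough unit the power exceeds 80%.

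Much of this stands. A reader might infer that the 80% is simply wrong, or that the sponsor is shown to have used the half-contrast. The documents support neither. The ICC is not a stated input, several pairings of analysis and ICC reach 80%, and so does a 54-v-54 comparison. A reader might also set the 0.60 SD excess beside the 0.40 main effect and call the assumed interaction 1.5 times as large. That compares a difference of simple effects with a marginal effect; on one common scale the figures are 0.30 and 0.40.

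The reply does not remove the point. The SAP itself attaches d = 0.30 to the Aim 1 interaction, and Aim 1 and Protocol 4.2 speak of benefit beyond a sum. If half-contrast scaling was meant, the text has to say so. The one slope unit computed here that exceeds 80% implies 0.90 SD by week 72, which is hard to describe as a minimal effect.

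**Conclusion.** The concern holds as a conditional one. If d = 0.30 is the excess over additivity in SD units at a follow-up visit, the stated 80% is not delivered: about 30% to 61% at ICC 0 across the analyses computed, and less with any clustering. If d is a half-contrast, the 80% is correct on that scale, but it refers to an excess of 0.60 SD, and an excess of 0.30 SD has 29% power. Which case applies cannot be settled from the documents.

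The factor of two between the standard errors is exact for equal cells. The percentages rest on r = 0.7 at all lags, a two-sided test, a visit-level SD and assumed ICCs; they are illustrations, not bounds. It does not follow that the trial has 29% power for its interaction as a settled fact, or that the main-effect power is wrong: power above 90% at d = 0.40 holds for marginal effects, but not for simple effects under 0/1 coding in the single-follow-up analyses.

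**What to change.** Leave N, the model and the tests as they are, and amend the SAP text:

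- State the contrast to which d = 0.30 refers, the coding of Move, Mind and MindMoves, the time scale of the slope, the SD behind d, and the ICC and variance formula behind the design effect.
- Recompute from the sponsor's own ICC and formula. Replace the single 80% with two figures: power for an excess over additivity of 0.30 SD, and the excess detectable with 80% power. If the half-contrast was used, these are about 29% and 0.60 SD.
- Justify the claim that the interaction effect is a reasonable minimum on that scale, or remove it, without comparing a difference of simple effects with a marginal main effect.
- Say that the main-effect power above 90% applies to marginal effects, and that 0/1 coding would turn the Move and Mind terms into simple effects with about 77-83% (single follow-up, ICC 0).

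The cost is a few sentences and one recomputation. The downside for the sponsor is that the stated interaction power probably becomes less favourable.
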